11.1. DERIVATIONS

- BMI expressed in kg/m²:

Weight (kg)/ height (m)².

- Time since initial onset of schizophrenia, expressed in years:

(Date of Informed Consent - Date of initial onset of schizophrenia <observed or imputed [see [APPENDIX 2](#)]>) / 365.25

Note: Round to one decimal place for each subject's calculated duration.

- Age at initial onset of schizophrenia, expressed in years:

(Date of initial onset of schizophrenia <observed or imputed [see [APPENDIX 2](#)]> - Date of birth + 1)/365.25

Note: Round to one decimal place for each subject's calculated age.

- Time since schizophrenia diagnosis, expressed in years:

(Date of Informed Consent - Date of schizophrenia diagnosis <observed or imputed [see [APPENDIX 2](#)]>)/365.25

Note: Round to one decimal place for each subject's calculated duration.

- Time since last acute exacerbation of schizophrenia, expressed in days:

Date of Informed Consent - Date of last acute exacerbation of schizophrenia <observed or imputed [see [APPENDIX 2](#)]>

Document: **CCI** 

Author: **PPD** 

Version Number: 0.6

Version Date: 30JAN2023

Template No.: CS_TP_BS016 Revision 6

Reference: CS_WI_BS005

Effective Date: 02Dec2019

Note: Round to one decimal place for each subject's calculated duration.

- Time since first hospitalization for treatment of schizophrenia, expressed in years:

(Date of Informed Consent – Date of first hospitalization for treatment of schizophrenia <observed or imputed [see [APPENDIX 2](#)])/365.25

Note: Round to one decimal place for each subject's calculated duration.

- Age at first hospitalization for treatment of schizophrenia, expressed in years:

(Date of first hospitalization for treatment of schizophrenia <observed or imputed [see [APPENDIX 2](#)] -

Date of birth + 1)/365.25

Note: Round to one decimal place for each subject's calculated age.

- Time since first anti-psychotic drug therapy of at least 2 weeks duration intended for treatment of schizophrenia, expressed in years:

(Date of Informed Consent - Start date of first anti-psychotic drug therapy of at least 2 weeks duration <observed or imputed [see [APPENDIX 2](#)])/365.25

Note: Round to one decimal place for each subject's calculated duration.

- Age at first anti-psychotic drug therapy of at least 2 weeks duration intended for treatment of schizophrenia, expressed in years:

(Start date of first anti-psychotic drug therapy of at least 2 weeks duration <observed or imputed [see [APPENDIX 2](#)] - Date of birth + 1)/365.25

Note: Round to one decimal place for each subject's calculated age.

12. MEDICAL HISTORY

Unless otherwise specified, the medical and surgical history summary tables will include the following columns: SEP-363856 50 to 100 mg/day, Quetiapine XR 400 to 800 mg/day, and Total.

Medical and surgical history information, including both past and concomitant medical conditions and major surgical history, as collected on the "Medical History" CRF form, will be coded using MedDRA

Document: **CCI**

Author: **PPD**

Version Number: 0.6

Version Date: 30JAN2023

Template No.: CS_TP_BS016 Revision 6

Reference: CS_WI_BS005

Effective Date: 02Dec2019

Version 22.0, and presented by SOC and PT for the SAF population by the actual treatment group. Data will be sorted by SOC based on the internationally agreed order (see [APPENDIX 10](#)) and by PT in decreasing frequency in the “SEP-363856 50 to 100 mg/day” column.

13. MEDICATIONS

Unless otherwise specified, the medications summary tables will include the following columns: SEP-363856 50 to 100 mg/day, Quetiapine XR 400 to 800 mg/day, and Total.

Medications will be coded to Anatomical Therapeutic Chemical (ATC) Levels and Preferred Names according to World Health Organization Drug (WHODRUG) dictionary, Version 01MAR2019.

Whenever available, the time information should be accounted for in the derivation of prior, concomitant, and post-treatment medications. See [APPENDIX 2](#) for the handling of partial dates for medications. In the case where it is not possible to define a medication as prior, concomitant, or post treatment, the medication will be classified by the worst case, i.e. concomitant.

- Prior medications are medications which stopped prior to the first dose of study medication.
- Concomitant medications are medications which started at the same time of or after the first dose of study medication and at the same time of or before the last dose of study medication; or started prior to and ended at the same time of or after the first dose of study medication; or started at the same time of or prior to the last dose of study medication and marked as ongoing.
- Post-treatment medications are medications which started after the last dose of study medication.

Prior and concomitant medication use will be summarized by ATC Level 3 and Preferred Base Name for the SAF population by the actual treatment group. Medications will be sorted by ATC Level 3 alphabetically and by Preferred Base Name in decreasing frequency in the “SEP-363856 50 to 100 mg/day” column.

Prior, concomitant, and post-treatment medications will be provided in data listings.

Psychotropic and/or Sedating Medications taken by subjects prior to each visit as collected on the “*Timing of last dose of Psychotropic and/or Sedating Medications*” CRF form will be summarized by ATC Level 3 and Preferred Base Name for the SAF population by the actual treatment group and visit.

Document: **CCI**

Author: **PPD**

Version Number: 0.6

Version Date: 30JAN2023

Template No.: CS_TP_BS016 Revision 6

Reference: CS_WI_BS005

Effective Date: 02Dec2019

14. STUDY MEDICATION EXPOSURE

Unless otherwise specified, the study medication exposure summary tables will include the following columns: SEP-363856 50 to 100 mg/day, Quetiapine XR 400 to 800 mg/day, and Total.

Exposure to study medication data will be summarized for the SAF population by the actual treatment group.

If a subject takes treatment that is not their planned treatment for a period of time, that period of other drug exposure will not be included in the various exposure and compliance summaries. However, this information will be presented with the subject specific listings.

The date/time of first dose of study drug and date/time of last dose of study drug will be respectively derived as the earliest (“Date Dosing Started” & “Time Dosing Started”) pair and the latest (“Date Dosing Ended” & “Time Dosing Ended”) pair as collected on the “*Study Drug Administration / Drug Accountability*” CRF form. The start and end dates/times from blister cards with the number of tablets dispensed equal to the (number of tablets returned + number of tablets reported lost) are excluded from the derivation.

Duration of exposure (in days) will be summarized both as a continuous variable for the double-blind treatment period and categorically:

- Number and percentage of subjects with exposure ≥ 1 , ≥ 14 , ≥ 28 , ≥ 42 , ≥ 90 , ≥ 120 , ≥ 150 , ≥ 180 , ≥ 270 , and ≥ 360 days;
- Number and percentage of subjects with exposure for 1 to 13, 14 to 27, 28 to 41, 42 to 89, 90 to 119, 120 to 149, 150 to 179, 180 to 269, 270 to 359 and ≥ 360 days

Total person-years of exposure will be calculated for each treatment group and overall for all subjects.

Mean daily dose and modal daily dose will be calculated for the entire double-blind treatment period and summarized.

The dose adjustment decision at each visit will be summarized in a shift table.

Lastly, the number of days that a subject received SEP-363856 50, 75, 100 mg/day, Quetiapine XR 300, 400, 600 and 800 mg/day dose level will be summarized for the SAF population both as a continuous variable and categorically:

Document: CCI

Author: PPD

Version Number: 0.6

Version Date: 30JAN2023

Template No.: CS_TP_BS016 Revision 6

Reference: CS_WI_BS005

Effective Date: 02Dec2019

- Number and percentage of subjects with exposure to a particular dose level for 1 to 13, 14 to 27, 28 to 41, 42 to 89, 90 to 119, 120 to 149, 150 to 179, 180 to 269, 270 to 359 and ≥ 360 days

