5.1. SAFETY (SAF) POPULATION

The safety (SAF) population will consist of all subjects who were enrolled and received at least one dose

Document: CCI

Author: PPD

Version Number: 0.6

Version Date: 30JAN2023

Template No.: CS_TP_BS016 Revision 6

Reference: CS_WI_BS005

Effective Date: 02Dec2019

of study drug during the 52-week treatment period. The SAF population will be used for the long-term safety and tolerability analyses. Subjects will be analyzed according to the actual treatment received. The actual treatment group will be determined as follows:

- For subjects randomized to the SEP-363856 50 to 100 mg/day group:
 - If a subject took at least one dose of SEP-363856 treatment during the entire double-blind treatment period, then the actual treatment group = SEP-363856 50 to 100 mg/day.
 - If a subject took only Quetiapine XR treatment during the entire double-blind treatment period, then the actual treatment group = Quetiapine XR 400 to 800 mg/day.
- For subjects randomized to the Quetiapine XR 400 to 800 mg/day group:
 - If a subject took at least one dose of Quetiapine XR treatment during the entire double-blind treatment period, then the actual treatment group = Quetiapine XR 400 to 800 mg/day.
 - If a subject took only SEP-363856 treatment during the entire double-blind treatment period, then the actual treatment group = SEP-363856 50 to 100 mg/day.

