14.1. DERIVATIONS

- For subjects randomized to the SEP-363856 group, a titration card is dispensed at Visit 2 which contains:
 - 3 capsules of 50 mg dose level and 3 capsules of placebo for 3 days
 - 6 capsules of 75 mg dose level and 6 capsules of placebo for 6 days

Drug accountability data is not separately collected for these dose levels at Visit 2. For subjects who were dispensed the titration card at Visit 2, the following assumptions will be made during analysis:

- The first six out of the total number of capsules a subject receives during the Visit 2 treatment period are assumed to be 3 of 50 mg and 3 capsules of placebo. The other capsules are assumed to be half 75 mg and half placebo.

Examples are:

- If a subject randomized to the SEP-363856 group took 6 capsules during the Visit 2, the cumulative dose is 150 mg ($= 50 \text{ mg} * 3 + 0 \text{ mg} * 3$).
- If a subject randomized to the SEP-363856 group took 8 capsules during the Visit 2, the cumulative dose is 225 mg ($= 50 \text{ mg} * 3 + 0 \text{ mg} * 3 + 75 \text{ mg} * 1 + 0 \text{ mg} * 1$).

- For subjects randomized to the Quetiapine XR group, a titration card is dispensed at Visit 2 which contains:
 - 2 capsules of 300 mg dose level and 2 capsules of placebo for 2 days
 - 2 capsules of 400 mg dose level and 2 capsules of placebo for 2 days
 - 5 capsules of 300 mg dose level and 5 capsules of 300 mg for 5 days

Drug accountability data is not separately collected for these dose levels at Visit 2. For subjects who were dispensed the titration card at Visit 2, the following assumptions will be made during analysis:

Document: CCI

Author: PPD

Version Number: 0.6

Version Date: 30JAN2023

Template No.: CS_TP_BS016 Revision 6

Reference: CS_WI_BS005

Effective Date: 02Dec2019

- The first four out of the total number of capsules a subject receives during the Visit 2 treatment period are assumed to be 2 capsules of 300 mg and 2 capsules of placebo. The next four out of the total number of capsules a subject receives during the Visit 2 treatment period are assumed to be 2 capsules of 400 mg and 2 capsules of placebo. The other capsules are assumed to be 300 mg.

Examples are:

- If a subject randomized to the Quetiapine XR group took 4 capsules during the Visit 2, the cumulative dose is 600 mg ($= 300 \text{ mg} * 2 + 0 \text{ mg} * 2$).

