17.1.1.3. Duration of Exposure

Duration of exposure to study medication at earliest onset is categorized below:

1 to 13, 14 to 27, 28 to 41, 42 to 89, 90 to 179, 180 to 269, 270 to 359 and ≥ 360 days.

If a subject reported an AE more than once within the same SOC/ PT in different exposure categories, the subject will be assigned to a category for that SOC/ PT based on the earliest onset. Event counts will not be included in this summary.

Denominators for exposure intervals will be based on the number of subjects who were exposed as of the first day of the interval. For cases where events start after the last dose, the exposure interval for the event will be considered the interval of the last day of exposure to study medication.

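### SAP 14 removes any drug that was not the planned treatment, so a subject reassigned under SAP 5.1 could have AEs in a column but no exposure in any summary table

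*SAP*

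**What the plan says.** SAP 5.1 analyses the safety population by treatment actually received and provides for complete mix-ups. For subjects randomised to SEP-363856: "If a subject took only Quetiapine XR treatment during the entire double-blind treatment period, then the actual treatment group = Quetiapine XR", with a mirror rule for the other arm. A subject who took even one dose of the randomised drug stays in the randomised column. SAP 17 bases all safety outputs on this population.

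SAP 14 uses the same columns: "Exposure to study medication data will be summarized for the SAF population by the actual treatment group". It then states that, for anyone who "takes treatment that is not their planned treatment for a period of time, that period of other drug exposure will not be included". The exclusion covers the exposure and compliance summaries, and the SAP adds: "However, this information will be presented with the subject specific listings". SAP 15 also presents compliance by actual group.

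SAP 14.1 takes duration as last administration date minus first, plus 1, and person-years as total days divided by 365.25. Mean daily dose (14.1) and percent compliance (15.1) both have duration in the denominator. The Visit 2 dose assumptions are set out by randomised arm, for example "For subjects randomized to the Quetiapine XR group, a titration card is dispensed at Visit 2". The example for the Weeks 2 to 52 middle-dose card works from the card that was dispensed.

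**The concern.** SAP 5.1 lets the column follow the drug taken. SAP 14 removes drug according to what was planned. The two rules agree for every subject except the one whom SAP 5.1 reassigns. For that subject, if planned means randomised, the whole treatment period is on non-planned drug and is removed.

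The AE tables and the exposure, dose and compliance tables under one column heading would then describe different sets of subjects. A visible symptom would be that the row for at least 1 day of exposure falls short of the safety-population N, although membership requires at least one dose. The exposure tables are also where a reader looks to see how much drug stands behind the safety data, which is the purpose of this trial.

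**Working it through.** The plan states no figure on this point, so the check traces the rules and then bounds the size.

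**Meaning of planned treatment.** The SAP does not define it. SAP 5.1 contrasts randomised with actual treatment, SAP 14.1 sets out its titration assumptions by randomised arm, and Protocol 15.3.2 computes mean daily dose for the drug given by randomisation. Randomised is therefore the natural reading, though not the only one.

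**Wholly mis-treated subject** (randomised to SEP-363856, took only quetiapine XR), on that reading:
- AEs and the safety denominator: quetiapine XR column (SAP 5.1, 17).
- Duration, person-years, mean and modal dose, days at each dose level, compliance: excluded for every day, so zero or missing in both columns and in Total (SAP 14, 15).
- Listings: exposure shown.

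**Partly mis-treated subject:** stays in the randomised column with all AEs. SAP 14 removes the days on the other drug, but the 14.1 duration formula has no term that does so. The rule and the formula give different answers.

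**Size.** Inputs: 300 subjects at 2:1, so about 200 on SEP-363856 and 100 on quetiapine XR; 52 weeks = 364 days.
- Person-years lost per wholly mis-treated subject, at most: 364/365.25 = 0.997.
- If that subject stops after 7 days: 7/365.25 = 0.019.
- Share of a column's person-years lost by k subjects at 364 days each, with n subjects averaging d days: k × 364/(n × d).

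The documents give neither k nor d. Assuming k = 1 to 3 and d = 120 to 364:
- Quetiapine XR: from 364/(100 × 364) = 1.0% to 1092/(100 × 120) = 9.1%.
- SEP-363856: from 364/(200 × 364) = 0.5% to 1092/(200 × 120) = 4.6%.
- One subject only: 1.0% to 3.0% and 0.5% to 1.5% respectively.

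The upper ends need full-year mix-ups in a column whose average exposure is only 120 days.

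**Titration card, if the period is counted.** The worked dose examples in 14.1 reproduce (150, 225, 600, 1400, 2000 and 225 mg). Seven days of the quetiapine XR card is 14 capsules:
- Dose taken: 300×2 + 400×2 + 600×3 = 3200 mg.
- Same 14 capsules under the SEP-363856 rule: 50×3 + 75×4 = 450 mg.

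**The case against.** The strongest reply is that the exclusion was written for partial mix-ups. It speaks of a period of time, and the sentence before it sets the frame as actual treatment group. The duration formula runs from first to last administration whatever the drug, so a programmer following 14.1 alone would give a wholly mis-treated subject full exposure in the right column. This stands in part: the loss is not certain. But nothing in the rule exempts a mix-up that lasts the whole period, and a text that supports two different tables needs settling.

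Four stronger readings are tempting and are not supported:
- *The subject has no exposure anywhere.* SAP 14 keeps the information in the subject listings. Only the summary tables are affected.
- *AE rates are distorted.* The SAP reports numbers and percentages of subjects, event counts and odds ratios. It specifies no AE rate per person-year.
- *The subject enters the numerator but not the denominator of AEs by duration of exposure.* SAP 17.1.1.3 sets its own rule, "Denominators for exposure intervals will be based on the number of subjects who were exposed as of the first day of the interval", and does not import the SAP 14 exclusion. The mismatch would arise only if the SAP 14 exposure variable were used there.
- *The plan already converts 3200 mg to 450 mg.* If the period is excluded, no dose is computed for the summaries. The two errors cannot occur together. The keying is also not uniform: 14.1 refers at one point to subjects who were dispensed the titration card.

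**Conclusion.** The point holds as a small inconsistency between two written rules. It rests on reading planned as randomised and on at least one subject having taken only the other drug. SAP 5.1 provides for that case, but the documents do not say that it occurred.

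Given both, each such subject would be missing from the exposure, dose and compliance summaries of the column that holds their AEs. The cost is at most about 1 person-year each, and far less after an early stop. The AE incidence estimates, including the primary endpoint, are unaffected.

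**What to change.** 1. In SAP 14, replace the reference to planned treatment with *not their actual treatment group as defined in Section 5.1*. A wholly mis-treated subject then contributes exposure to the column that holds their AEs, up to 0.997 person-years.
2. In 14.1 and 15.1, make the duration, dose and compliance formulas apply the same exclusion, so that days on the other drug leave both numerator and denominator for partly mis-treated subjects. The existing adjustment for visits with missing accountability data is a ready model.
3. As a consequence of counting these periods, key the Visit 2 titration-card assumptions in 14.1 to the card dispensed, as the Weeks 2 to 52 example already does.
4. If the SAP 14 exposure variable is to be used in 17.1.1.3, say so there.

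The cost is a few wording changes. Cards carry unique identifiers and are assigned through the IWRS (Protocol 9.2.1, 9.4), so no new data are needed. The final analysis follows unblinding (SAP 4.3), so using card identity does not threaten the blind. Results for correctly treated subjects do not change.

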14.1. DERIVATIONS

- For subjects randomized to the SEP-363856 group, a titration card is dispensed at Visit 2 which contains:
 - 3 capsules of 50 mg dose level and 3 capsules of placebo for 3 days
 - 6 capsules of 75 mg dose level and 6 capsules of placebo for 6 days

Drug accountability data is not separately collected for these dose levels at Visit 2. For subjects who were dispensed the titration card at Visit 2, the following assumptions will be made during analysis:

- The first six out of the total number of capsules a subject receives during the Visit 2 treatment period are assumed to be 3 of 50 mg and 3 capsules of placebo. The other capsules are assumed to be half 75 mg and half placebo.

Examples are:

- If a subject randomized to the SEP-363856 group took 6 capsules during the Visit 2, the cumulative dose is 150 mg ($= 50 \text{ mg} * 3 + 0 \text{ mg} * 3$).
- If a subject randomized to the SEP-363856 group took 8 capsules during the Visit 2, the cumulative dose is 225 mg ($= 50 \text{ mg} * 3 + 0 \text{ mg} * 3 + 75 \text{ mg} * 1 + 0 \text{ mg} * 1$).

- For subjects randomized to the Quetiapine XR group, a titration card is dispensed at Visit 2 which contains:
 - 2 capsules of 300 mg dose level and 2 capsules of placebo for 2 days
 - 2 capsules of 400 mg dose level and 2 capsules of placebo for 2 days
 - 5 capsules of 300 mg dose level and 5 capsules of 300 mg for 5 days

Drug accountability data is not separately collected for these dose levels at Visit 2. For subjects who were dispensed the titration card at Visit 2, the following assumptions will be made during analysis:

Document: CCI

Author: PPD

Version Number: 0.6

Version Date: 30JAN2023

Template No.: CS_TP_BS016 Revision 6

Reference: CS_WI_BS005

Effective Date: 02Dec2019

- The first four out of the total number of capsules a subject receives during the Visit 2 treatment period are assumed to be 2 capsules of 300 mg and 2 capsules of placebo. The next four out of the total number of capsules a subject receives during the Visit 2 treatment period are assumed to be 2 capsules of 400 mg and 2 capsules of placebo. The other capsules are assumed to be 300 mg.

Examples are:

- If a subject randomized to the Quetiapine XR group took 4 capsules during the Visit 2, the cumulative dose is 600 mg ($= 300 \text{ mg} * 2 + 0 \text{ mg} * 2$).
- If a subject randomized to the Quetiapine XR group took 8 capsules during the Visit 2, the cumulative dose is 1400 mg ($= 300 \text{ mg} * 2 + 0 \text{ mg} * 2 + 400 \text{ mg} * 2 + 0 \text{ mg} * 2$).
- If a subject randomized to the Quetiapine XR group took 10 capsules during the Visit 2, the cumulative dose is 2000 mg ($= 300 \text{ mg} * 2 + 0 \text{ mg} * 2 + 400 \text{ mg} * 2 + 0 \text{ mg} * 2 + 300 \text{ mg} * 2$).
- Study drug will be provided in one-week blister cards containing 18 capsules arranged in 9 columns and 2 rows. In addition to the above assumptions, it is also established that capsules are taken starting from left (day 1) to right (extra day) and from top (row 1) to bottom (row 2).

An example is:

Weeks 2 to 52: Blinded Middle Dose (from protocol Section 9.2.1)

Day	1	2	3	4	5	6	7	Extra day	Extra day
Row 1	SEP-363856 75 mg or QXR 300 mg								
Row 2	Placebo Or QXR 300 mg								

- If the above blister card of SEP-36385 was dispensed and a subject took 5 capsules, the cumulative dose is 225 mg ($= 75 \text{ mg} * 3 + 0 \text{ mg} * 2$).
- Duration of exposure (days) = date of last study medication administration – date of first study

Document: **CCI**

Author: **PPD**

Version Number: **0.6**

Version Date: **30JAN2023**

Template No.: **CS_TP_BS016 Revision 6**

Reference: **CS_WI_BS005**

Effective Date: **02Dec2019**

medication administration + 1. Interruptions in exposure (i.e. missed doses) and dose changes (if any) are not considered in the calculation of overall exposure.

- Total person-years of exposure is the sum of all durations of exposure in days / 365.25.
- Mean daily dose (mg/day):

$$\frac{\sum \text{Dose per capsule for Visit } j * (\# \text{ Capsules Dispensed for Visit } j - \# \text{ Capsules Returned for Visit } j - \# \text{ Capsules Lost for Visit } j)}{\text{Duration of Exposure}}$$

At Visit 2, for subjects who were dispensed the titration card with mixed dose levels, please refer to the first and the second bullet in this current section for assumptions to be used in dose calculation. At all visits, please refer to the third bullet in this current section for an assumption to be used in dose calculation.

If the number of capsules dispensed, returned, and/or lost as collected on the *“Study Drug Administration / Drug Accountability”* CRF form is missing for one or more visits, the mean daily dose will be calculated based on visits with complete drug accountability data available. That is, the numerator of the formula above will only include visits with the number of tablets dispensed, returned, and lost available, and the denominator should be adjusted to exclude dosing periods covered by visits excluded from the calculation (i.e., Duration of Exposure – dosing periods [sum of [EXENDTC – EXXTDTC+1]] covered by visits with missing or incomplete accountability data). If the dose level of a visit is unknown, that visit should be excluded from the calculation as well in both the numerator and the denominator.

- Modal daily dose will be determined as the daily dose that is taken for the most time (in terms of number of days) among all doses taken. A subject’s modal daily dose may fall in one of the categories below:
 - SEP-363856 50 mg/day
 - SEP-363856 75 mg/day
 - SEP-363856 100 mg/day
 - Quetiapine XR 300 mg/day
 - Quetiapine XR 400 mg/day
 - Quetiapine XR 600 mg/day

Document: **CCI**Author: **PPD**

Version Number: 0.6

Version Date: 30JAN2023

Template No.: CS_TP_BS016 Revision 6

Reference: CS_WI_BS005

Effective Date: 02Dec2019

- Quetiapine XR 800 mg/day
- Tie between xx and yy (i.e. the subject was on xx mg/day and yy mg/day for the same amount of time) (if needed)

